## 5.0 STUDY DESIGN AND METHODS

### 5.1 Design/Study Type

Non-treatment intervention, randomized clinical trial of up to 350 participants [244 patient participants plus up to 106 of their caregivers as caregiver participants] (social behavioral research).

### 5.2 Selection of Instruments

Questionnaire-based instruments will be administered 1) in person by a trained research assistant at the time of a routinely scheduled visit, 2) by e-survey, 3) by phone, , or 4) by postal mail. Mode of collection will be recorded. REDCap (Research Electronic Data Capture) will be used to collect and store all participant information and survey answers. REDCap is a secure, web-based, HIPAA-compliant application hosted by the Partners HealthCare Research Computing, Enterprise Research Infrastructure & iServices (ERIS) group, designed to support data capture for research studies, providing: 1) an intuitive interface for validated data entry; 2) audit trails for tracking data manipulation and export procedures; 3) automated export procedures for seamless data downloads to common statistical packages; and 4) procedures for importing data from external sources.

Regardless of whether a participant is randomized to receive Usual IC materials or the Interventional IC materials, each participant will be asked complete three assessments:

#### **Instrument 1: Baseline Assessment (See Appendix C)**

The baseline assessment will assess socio-demographics, information/communication preferences, decision control preferences, and illness understanding. Patients will complete this assessment after consenting for the study, but before randomization. The baseline assessment takes approximately 5 minutes to complete.

**Title:** Improving Informed Consent for Palliative Chemotherapy: RCT of Usual IC versus Investigational IC

**Overall PI:** [name], Dana-Farber Cancer Institute

**Dana-Farber protocol version no./date:** v17 / August 30, 2017

### **Instrument 2: Post-Decision Assessment (See Appendix E and Appendix F)**

Within 0-4 weeks of the participant's treatment decision, the participant will be asked to complete a post-decision survey assessing core understanding required for informed consent (IC) (risks, benefits, alternatives), understanding of illness (diagnosis, curability), decisional conflict, satisfaction with the IC materials, satisfaction with communication, and anxiety. The post-decision assessment takes approximately 20 minutes to complete.

### **Instrument 3: Follow-up Assessment (See Appendix G and Appendix I)**

Within 2-3 months of the participant's treatment decision, the participant will be asked to complete a follow-up survey assessing changes in treatment and illness understanding, decisional regret, communication satisfaction, care satisfaction & anxiety. The post-decision assessment takes approximately 20 minutes to complete.

**NOTE:** Participants will be asked questions about prognosis regardless of whether or not they skip the life expectancy sections in the booklet and video.

Immediately following completion of the follow up assessment: Using methods similar to those described by White et al, the interviewer will show each participant his/her responses to the 2 questions about prognosis\*\*. Next, the interviewer will read the following standardized prompt: "Please take a moment to look at your responses. I notice that your answers to these two questions are [different/the same]. Can you tell me a little bit about this?"

The research assistant will then ask permission to audio-record the patient's answers. If the participant is willing to answer the question but declines audio-recording, notes will be taken during and after the interview. The RA will use standard cognitive interviewing techniques, such as reflexive listening, "think alouds" and standard probes ("can you tell me what you mean by that?") as necessary.

*\*\*Copy-pasted for reference - these are the 2 questions about prognosis:*

*Q: Based on what you have learned or been told, what is your understanding about how long the typical person with your type of cancer can expect to live?*

*A: 1, More than 10 years | 2, More than 5, but less than 10 years | 3, More than 3, but less than 5 years | 4, More than 2, but less than 3 years | 5, More than 1, but less than 2 years | 6, Less than 1 year*

*Q: Every person is different and every situation is unique. If you had to make a guess - based on what you have learned about your cancer, your cancer treatment, and what you know about yourself - how long do you think that you have to live?*

*A: 1, More than 10 years | 2, More than 5, but less than 10 years | 3, More than 3, but less than 5 years | 4, More than 2, but less than 3 years | 5, More than 1, but less than 2 years | 6, Less than 1 year*

**Medical Record Abstraction (see Appendix K):** Research assistants will perform medical record abstraction. These medical record abstractions will be designed to assess relevant information about their clinical condition (e.g. stage at diagnosis, date of recurrence, performance status, comorbid conditions), treatment decision, and treatment experience. Information will be entered into a study specific structured medical record abstraction tool (Appendix K). See below for specific information

**Title:** Improving Informed Consent for Palliative Chemotherapy: RCT of Usual IC versus Investigational IC

**Overall PI:** [name], Dana-Farber Cancer Institute

**Dana-Farber protocol version no./date:** v17 / August 30, 2017

to be abstracted:

- date of diagnosis; stage at diagnosis; prior adjuvant or palliative chemotherapy; date of metastatic recurrence (if relevant); comorbid medical conditions; performance status; treatment decision made (e.g., what chemotherapy regimen, clinical trial, no chemotherapy); changes in treatment (e.g. dose reductions, change in chemotherapy); results of restaging scans (disease progression, stable disease, or response); changes in treatment; medical record documentation of advance care planning; and vital status at study completion.

**NOTE:** Each site has the option to conduct the medical record review for their site's participants using the unique study ID # and enter the information into REDCap using the participants' unique study ID #. Medical records from participating sites will not be released to Dana-Farber unless the participant signs the medical record release form (Appendix X).

In some cases, a participant will consent to participate in this study and begin this study while at a participating site, but then continue/transfer care at a non-participating site. In these instances, the participant will be asked to sign an optional, voluntary Global Medical Record Release Form (see Appendix X) so that the central research assistant at Dana-Farber can access the participant's medical records in order to complete the study Medical Record Abstraction (Appendix K).

**Each caregiver will be asked complete two assessments:**

**Instrument 1: Caregiver Baseline Assessment (See Appendix D)**

The baseline assessment will assess socio-demographics, information/communication preferences, and illness understanding. The baseline assessment takes approximately 5 minutes to complete.

**Instrument 2: Caregiver Follow-up Assessment (See Appendix H and Appendix J)**

Within 2-3 months of the participant's treatment decision, the participant will be asked to complete a follow-up survey assessing changes in treatment and illness understanding, decisional regret, communication satisfaction, care satisfaction & anxiety. The post-decision assessment takes approximately 20 minutes to complete.

**CAREGIVER:** Immediately following completion of the caregiver follow up assessment, the interviewer will read the following standardized prompt:

How do you think the person for whom you care would answer this question? Could you tell me a little bit about why you answered in this way?

*Q: Based on what you have learned or been told, what is your understanding about how long the typical person with your type of cancer can expect to live?*

*A: 1, More than 10 years | 2, More than 5, but less than 10 years | 3, More than 3, but less than 5 years | 4, More than 2, but less than 3 years | 5, More than 1, but less than 2 years | 6, Less than 1 year*

How do you think the person for whom you care would answer this question? Could you tell me a little bit about why you answered in this way?

*Q: Every person is different and every situation is unique. If you had to make a guess - based on what you have learned about your cancer, your cancer treatment, and what you know about yourself - how long do you think that you have to live?*

*A: 1, More than 10 years | 2, More than 5, but less than 10 years | 3, More than 3, but less than 5*

**Title:** Improving Informed Consent for Palliative Chemotherapy: RCT of Usual IC versus Investigational IC

**Overall PI:** [name], Dana-Farber Cancer Institute

**Dana-Farber protocol version no./date:** v17 / August 30, 2017

*years | 4, More than 2, but less than 3 years | 5, More than 1, but less than 2 years | 6, Less than 1 year*

The research assistant will ask permission to audio-record the caregiver's answers. If the participant is willing to answer the question but declines audio-recording, notes will be taken during and after the interview. The RA will use standard cognitive interviewing techniques, such as reflexive listening, "think alouds" and standard probes ("can you tell me what you mean by that?") as necessary.

**NOTE:** Caregivers will be asked questions about prognosis regardless of whether or not they skip the life expectancy sections in the booklet and video.

### 5.3 Description of Intervention

**Intervention Overview:** The intervention consists of 5 sets of chemotherapy informed consent (IC) tools. Each tool consists of a video and a complementary booklet which explain a common chemotherapy option for mCRC, locally advanced pancreatic cancer, or metastatic pancreatic cancer. This suite of tools reviews the following treatment options:

- IC Tool 1: FOLFOX & FOLFOX + bevacizumab are reviewed together in one IC tool, comprised of a video and complementary booklet
- IC Tool 2: FOLIRI & FOLFIRI + bevacizumab are reviewed together in one IC tool: comprised of a video and complementary booklet.
- IC Tool 3: FOLFIRINOX is reviewed in one IC tool: comprised of a video and complementary booklet.
- IC Tool 4: Gemcitabine + nab-paclitaxel is reviewed in one IC tool: comprised of a video and complementary booklet.
- IC Tool 5: Gemcitabine is reviewed in one IC tool: comprised of a video and complementary booklet.

➤ FOLFOX & FOLFOX + bevacizumab booklet – see Appendix N  
➤ FOLFOX & FOLFOX + bevacizumab video website – see Appendix O  
➤ FOLIRI & FOLFIRI + bevacizumab booklet – see Appendix P  
➤ FOLIRI & FOLFIRI + bevacizumab video website – see Appendix Q  
➤ FOLFIRINOX booklet – see Appendix R  
➤ FOLFIRINOX video website – see Appendix S  
➤ Gemcitabine + nab-paclitaxel booklet – see Appendix T  
➤ Gemcitabine + nab-paclitaxel video website – see Appendix U  
➤ Gemcitabine booklet – see Appendix V  
➤ Gemcitabine video website – see Appendix W

#### Description of informed consent (IC) videos

Each video is approximately 20 minutes and was filmed and edited by a professional health videographer. Videos and booklets are complementary but do not entirely overlap. DFCI oncologists and nurses narrate factual information about the chemotherapy regimen of interest. "B-roll" visually illustrates potentially confusing aspects of the chemotherapy regimen (for example: a chemotherapy home infusion pump). Candid patient interviews are interspersed throughout the video to present patients' experience, with particular attention to quality of life and coping.

**Title:** Improving Informed Consent for Palliative Chemotherapy: RCT of Usual IC versus Investigational IC

**Overall PI:** [name], Dana-Farber Cancer Institute

**Dana-Farber protocol version no./date:** v17 / August 30, 2017

Information about life expectancy is included as an optional link, allowing patients/caregivers a choice about whether or not to hear this information. Patients and providers in the video are diverse with respect to age, gender, and ethnicity. Videos will be accessible via a password-protected website suitable for viewing on tablet or computer.

The structure & content of the videos are outlined below.

- *Basics:* The drugs used as part of each regimen, their route of administration, schedule, logistics of administration. A nurse demonstrates a 5FU infusion pump.
- *Risks:* Toxicities reviewed, with greatest attention to the most common toxicities, followed by rare but serious complications. Side effects specific to bevacizumab highlighted.
- *Benefits:* State that chemo alone cannot cure mCRC, locally advanced pancreatic cancer, or metastatic pancreatic cancer, and review the palliative intent of chemotherapy.
- *Alternatives:* Mention other chemotherapy regimens, clinical trials, & palliative/supportive care.

### **Description of informed consent (IC) booklets**

Booklets are regimen-specific IC documents, which serve as a regimen-specific educational tool and an acceptable documentation of IC. Content of the written IC tool adheres to regulatory requirements of IC with attention to patients' information preferences. The tools are written at an 8th grade reading level, use generic drug names, and communicate risk clearly.

- *Basics:* The drugs used as part of each regimen is outlined, along with their route of administration.
- *Benefits:* Includes the purpose of treatment (palliative, prevent symptoms, not cure).
- *Impact on prognosis:* Patients have the option of reviewing a section that describes typical life-expectancy of mCRC with and without chemotherapy. This section is closed by a seal, and preceded by a warning to allow them to make a conscious choice of whether or not to be exposed to this information.
- *Risks:* Most common toxicities listed in order of frequency (and approximate rates). Rare complications listed, but de-emphasized to avoid the feel of a “laundry list.”
- *Alternatives:* Clinical trials, palliative /supportive care, & other chemotherapy regimens.
- *FAQ's:* Identified by patient stakeholders

### **Randomization and Administration of Intervention**

**Overview:** Patients randomized to the Usual IC Arm will undergo the standard institutional practice of informed consent for chemotherapy. At Dana-Farber, this will include receipt and signature of the standard institutional consent form for chemotherapy. The oncologist may also choose to give the patient the institutionally approved chemotherapy information sheets according to their preference (this is not a required practice at Dana-Farber).

### **Participating sites should follow their own institutional practices for usual informed consent.**

Patients randomized to Interventional IC Arm will be given regimen specific written and video Informed Consent tools developed by the study team. The treating oncologist will identify which chemotherapy regimen(s) are being considered, in order to select the appropriate informed consent (IC) tool(s) to give the patient. The patient may be given more than one IC tool if relevant; for example: if they are deciding between FOLFOX and FOLFIRI, they could be given both IC tools. Patients randomized to the intervention arm may receive the intervention in addition to OR in place of the

**Title:** Improving Informed Consent for Palliative Chemotherapy: RCT of Usual IC versus Investigational IC

**Overall PI:** [name], Dana-Farber Cancer Institute

**Dana-Farber protocol version no./date:** v17 / August 30, 2017

standard institutionally approved chemotherapy information sheets (both are acceptable); this is at the discretion of the treating site or the treating physician. Patients randomized to the Interventional IC Arm will undergo informed consent for chemotherapy. This will include receipt of the investigational IC tool for chemotherapy in addition to OR in place of the standard institutionally approved chemotherapy teaching sheet.

At the beginning of the study period, the video and booklet informed consent tools will be shared with medical oncologists and nurse practitioners at a GI oncology staff meeting. The purpose of this orientation is to help facilitate any subsequent conversations about the study informed consent (IC) tools that might occur between providers and patients randomized to the intervention.

**Timing of intervention:** Patients randomized to the experimental arm of the study will be exposed to the intervention as soon as possible following the oncology visit discussing treatment recommendations (see protocol schema on page 1) and *prior* to their actual chemotherapy decision and treatment initiation. In select cases in which it is not possible to administer the intervention prior to their initiation of chemotherapy (e.g. such as a patient who opts to start a new chemotherapy regimen on the same day as their treatment discussion), it will be allowed to administer the intervention within 2 weeks of chemotherapy initiation. Every attempt will be made to ensure that the intervention is given to the patient as soon as feasibly possible, to ensure that the information is most relevant to them.

**Administration of intervention:** A research assistant or the treating physician/nurse practitioner (depending upon the preference of the physician/nurse practitioner) will give the patient the relevant informed consent (IC) booklet(s) along with printed information containing the URL address and password to the relevant IC video(s). The research assistant will offer to meet the patient in the clinic in order to orient them to the booklet and to allow them to watch the video on a study iPad. If the patient prefers not to review the study materials in clinic (e.g. due to inconvenience of scheduling), the study materials will be mailed to the patients' home, and the research assistant will follow-up by phone to answer any questions about accessing the video. Patients will be encouraged to review the booklet(s)/video(s) as many times as they wish, and will be encouraged to discuss any questions with their oncologist.

## 5.4 Data Collection

### Summary of measures used at each patient assessment

Domain	Measures	Baseline Assessment	Post-Decision Assessment	Follow-up Assessment
Socio-demographics a	Standard assessments	• x		
Health Literacy and numeracy b	Stagliano  (2013), Lipkus  (2001)	• x		
QOL c	FACT-G 	•	•	•
Optimism d	Life Orientation Test-Revised 	•		
Distress e	Emotional wellbeing component of FACT-G 	•	•	•
Communication & decision preferences f	Control Preferences Scale 	•		
	Preferred information for chemotherapy decision (for study)	• x		
	Prognostic communication preferences, Meropol 	• x		
Illness understanding	Developed for study	• x		
Use of IC booklet and video	Video use monitored via password protected website, booklet use monitored by survey		•	• x
Quality of Informed Consentg				
Core Understanding				
Chemotherapy risks	Modified from Leighl et al 		•	
Chemotherapy benefits	Adapted from CANCORS  (primary outcome)		•	• x
Decision Making				

**Title:** Improving Informed Consent for Palliative Chemotherapy: RCT of Usual IC versus Investigational IC

**Overall PI:** [name], Dana-Farber Cancer Institute

**Dana-Farber protocol version no./date:** v17 / August 30, 2017

Adequate information	Developed for study			
Decisional involvement	Modified Control Preferences Scale 		•	
Decisional conflict	Modified SURE assessment 		•	
Satisfactionh				
MD-patient relationship	Revised Human Connection Scale 		• x	
With study IC tools/ standard IC	Developed for study		•	
With decision	Brehaut decisional regret scale 			•
Doctor-patient communicationi				
Patient-centered communication	Aurora and Mazor 		•	• x
Prognostic communication	Developed for study			• x
Prognostic Understanding j	Adapted from CANCORS 			• x
Advance Care Planning	Chart abstraction (DNR) and patient report (healthcare proxy)			• x

• Patient Participant Assessment

x Caregiver Participant Assessment

**Clinical characteristics:** Date of diagnosis (or metastatic recurrence), location of metastases, prior adjuvant chemotherapy, and ECOG performance status via chart review.

**aSocio-demographics:** Age, race/ethnicity, marital status, education, insurance status, preferred language, religious affiliation via chart review; and a one-item measure of religious coping via participant questionnaire.

**bHealth Literacy & Numeracy:** Participants will complete a validated 1-item screening measure for health literacy developed by Stagliano, and a validated 1-item screening measure to assess numeracy.

**cQOL:** QOL will be assessed by the well validated Functional Assessment of Cancer Therapy-General (FACT-G), a 27-item scale assessing physical wellbeing, social/family wellbeing, functional wellbeing, emotional wellbeing, and functional wellbeing.

**dOptimism:** The validated 7-item Life Orientation Test-Revised will assess trait optimism at baseline.

**eDistress:** will be measured using the emotional wellbeing subscale of the FACT-G QOL survey.

**fCommunication & decision-making preferences:**

Prognostic communication preferences: 5 items from an instrument developed by Meropol et al will assess patients' preferences regarding prognostic communication (e.g. "I want to hear detailed statistics," "I want the doctor to speak to me in a positive manner") via participant questionnaire. Responses: "strongly agree," to "strongly disagree" on a 5-point scale.

Preferred information for chemotherapy decision: 7 items developed for the study will assess the amount of information patients want about each of the following topics relevant to chemotherapy informed consent: potential side effects, other treatment options, potential impact on quality of life, likelihood of cancer control, likelihood of cure, impact on length of life. Response options are on a 5-point Likert scale ranging from no information to as much information as possible.

Preferred involvement in care decisions: The Control Preferences Scale is a validated 2-item measure of preferences for decision involvement (active, active-shared, collaborative, passive

**Title:** Improving Informed Consent for Palliative Chemotherapy: RCT of Usual IC versus Investigational IC

**Overall PI:** [name], Dana-Farber Cancer Institute

**Dana-Farber protocol version no./date:** v17 / August 30, 2017

shared, or passive) via participant questionnaire.

### **Quality of Informed Consent:**

Understanding of chemotherapy benefits: The first primary outcome is a validated item from CANCORS. Patients are asked: “After talking with your doctors about chemotherapy, how likely did you think it was that chemo would cure your cancer?” Responses (“very likely,” “somewhat likely,” “a little likely,” “not at all likely,” “don’t know”) will be dichotomized to accurate (“not at all likely”) and inaccurate (all others). The pre-specified time-point for assessing the primary outcome is at the follow-up assessment, although patients will also be asked this question at baseline and the post-decision survey. Similar to CanCORS, patients will also be asked how likely they think it is that chemotherapy will “help you with problems or symptoms you are having because of your cancer,” “control the growth of your cancer,” and “help you live longer.” These additional items are included in the post-decision survey alone.

To assess understanding of treatment goal, patients are asked at the post-decision survey, “according to your doctor, what is the goal of the chemotherapy?” with the ability to choose any/all of the following response options: cure, control cancer growth, alleviate symptoms, prolong life, or other. Selecting either control cancer growth, and/or alleviate symptoms, and/or prolong life are defined as accurate understanding; “to cure” was inaccurate.

Understanding of chemotherapy risks: Modified items from Leighl et al will assess patients’ understanding of the potential risks (e.g. side effects) of their chemotherapy choice via participant questionnaire. These items include understanding of key risks (e.g., FOLFOX+/-bevacizumab (e.g. fatigue, nausea/vomiting and neuropathy), and FOLFIRI+/-bevacizumab (e.g. fatigue, nausea/vomiting, diarrhea, hair loss)). The accuracy of patients’ understanding of chemotherapy risks will be scored based upon the chemotherapy regimen they opted to receive, as described below:

- Patients initiating FOLFOX or FOLFOX bev will be considered to have an accurate understanding of risks if they respond that they are somewhat/very likely to experience neuropathy and nausea and a little/not very likely to experience hair loss  
We will create similar algorithms for all of the other chemotherapy regimens based upon well-established toxicity profiles.

Adequate information for informed consent (IC): Patients will be asked whether they received the amount of information they desired regarding the following topics: potential side effects, management of side effects, potential impact on QOL, other treatment options, likelihood of cancer control, likelihood of cure, and potential impact on length of life, using a 5-point Likert scale from too far little information to far too much information.

Decisional Conflict & Decisional Control: Decisional conflict (representing potential conflict and satisfaction about a medical decision) will be assessed using a modified 6-item version of the SURE assessment, which measures whether patients feel sure about what matters to them, understand their treatment options, understand the risks/benefits of those options, and feel supported in their decision.

Achievement of decisional control preferences (i.e. achievement of preferred role in treatment decision-

**Title:** Improving Informed Consent for Palliative Chemotherapy: RCT of Usual IC versus Investigational IC

**Overall PI:** [name], Dana-Farber Cancer Institute

**Dana-Farber protocol version no./date:** v17 / August 30, 2017

making) will be assessed using the modified Control Preferences Scale (decisional involvement is compared with stated preferences).

Decisional regret: Brehaut's validated 5-item scale will measure decision regret (scale 0-100).

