*Hypothesis:* Patients randomized to the intervention will be more likely to discuss their end-of-life care preferences with their healthcare proxy, and with their oncologist as compared to patients randomized to the usual IC process.

We will adhere to standard reporting principles delineated by the CONSORT statement for conduct and reporting of randomized trials. Primary reports will reflect the as randomized, "intention to treat" principle, however, we will also describe results according to actual exposure to the study interventions (based on patients' self-report of whether they reviewed the standard-of-care, or investigational chemotherapy informed consent materials). Fisher's exact test will test the difference between the study arms in the first primary outcome (the proportion of patients at follow-up assessment who fail to understand that chemotherapy is "not at all likely" to cure their cancer, as assessed by an item from CANCORS). We will also test the influence of the intervention on secondary outcomes (e.g. understanding of the goal of palliative chemotherapy, chemotherapy risks, decisional conflict,

**Title:** Improving Informed Consent for Palliative Chemotherapy: RCT of Usual IC versus Investigational IC

**Overall PI:** [name], Dana-Farber Cancer Institute

**Dana-Farber protocol version no./date:** v17 / August 30, 2017

achievement of preferred role in decision-making, satisfaction with chemotherapy IC process, prognostic understanding, advance care planning, discussion of end-of-life care preferences, satisfaction with MD communication, satisfaction with informed consent (IC) documents, decisional regret, emotional distress) using Fisher's exact or chi-square tests for dichotomous outcomes, and t-tests or Wilcoxon tests for linear outcomes. For missing data for primary or secondary outcomes, we will employ multiple imputation under a missing at random assumption.

Subset analyses will explore the effect of the intervention on 1) patients making a decision about 1st line treatment, 2) patients making a decision about 2nd line treatment, 3) patients with colorectal cancer, and 4) patients with pancreatic cancer.

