Because the effects of our intervention may be moderated by patient characteristics (e.g. age, race/ethnicity, health literacy and numeracy, communication preferences, decisional control preferences), we plan to conduct exploratory analyses investigating whether these factors moderate the effect of the intervention on outcomes including 1) accurate understanding of chemotherapy benefits, 2) satisfaction with communication and the IC tools, 3) decisional involvement, or 4) emotional distress. For example: we hypothesize that the IC tool may lead to decreased distress among patients who prefer a detail-oriented prognostic communication style, whereas it may lead to increased distress among patients who prefer a vague and support-focused prognostic communication style. We would also hypothesize that the effects of

**Title:** Improving Informed Consent for Palliative Chemotherapy: RCT of Usual IC versus Investigational IC

**Overall PI:** [name], Dana-Farber Cancer Institute

**Dana-Farber protocol version no./date:** v17 / August 30, 2017

the intervention may be greater among patients with higher health literacy scores. We will test these hypotheses using multivariable logistic or linear regression analyses (depending upon the dependent variable), including interaction terms for collinear factors, and controlling for potential confounding factors (e.g. age, race/ethnicity, marital status).

**Power:** In the CANCORS study, 80% of mCRC patients on 1st line chemotherapy thought that chemotherapy could potentially cure their disease (median of 4 months post-diagnosis). Based on previous series and projections about our patient mix, we anticipate that 60% of patients will have inaccurate expectations about the benefits of chemotherapy. If the intervention strategy is able to better align expectations with likely outcomes by one third (33%) we will deem the intervention as having major impact. If this benchmark 33% reduction is not achieved but the intervention exposed subjects nonetheless have expectations that are more accurate, we will view the intervention as beneficial but lacking major impact. Assuming a baseline 60% rate of inaccurate expectations about the benefits of chemotherapy, with a total of 194 patients, we will have 80% power to detect a 33% decrease (20% absolute decrease) in inaccurate expectations among patients exposed to the intervention with a one-sided type I error of 2.5%.

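### The cure question is said to be asked at baseline, but the measures table does not show it there, and the primary test makes no use of the answer

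*Combined protocol and SAP*

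**What the plan says.** - **Section 5.4, Quality of Informed Consent.** The primary item asks how likely the patient thinks it is that chemotherapy will cure the cancer; only the answer that cure is not at all likely counts as accurate. Follow-up is the primary time point, "although patients will also be asked this question at baseline and the post-decision survey".
- **Section 5.4, summary of measures table.** The chemotherapy-benefits row, labelled "primary outcome", has marks under post-decision and follow-up and none under baseline. Illness understanding is a separate row, developed for the study, and is marked at baseline.
- **Section 5.2, Instrument 1.** "The baseline assessment will assess socio-demographics, information/communication preferences, decision control preferences, and illness understanding". Section 5.7 (Questionnaire Administration) repeats this. Neither names the cure item.
- **Section 5.2, Instrument 2.** The post-decision survey covers "understanding of illness (diagnosis, curability") as one domain, listed apart from risks, benefits and alternatives.
- **Section 6.0.** "Fisher's exact test will test the difference between the study arms in the first primary outcome", on the proportion inaccurate at follow-up. Missing outcomes are handled by multiple imputation under missing at random, with no imputation variables named. The baseline cure answer is not named in the primary test, the moderator models or the imputation plan.
- **Timing.** Instrument 1 puts the baseline survey before randomization. Section 5.5, step 3, lets some patients complete it up to two weeks afterwards. Section 3.0 lets patients already on first-line treatment enrol and complete baseline, with randomization at their next treatment decision.

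**The concern.** Two things need attention. First, the protocol gives two answers on whether the item behind its primary endpoint is measured at baseline. A baseline form built from the table could leave out a question that the text promises.

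Second, even if the answer is collected, the primary comparison does not use it. A patient's earlier answer to the same question is a natural predictor of the later one. Conditioning on it would sharpen the arm comparison, remove the effect of a chance baseline imbalance on the estimate, and help to impute missing follow-up answers. Section 5.1 enrols 244 patients and Section 6.0 powers on 194. The gap is 50/244, or 20.5%, so a fair amount of imputation may be needed, although no dropout rate is stated.

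**Working it through.** **Inputs from the documents.** Control rate 60% inaccurate (Section 6.0: "Assuming a baseline 60% rate of inaccurate expectations about the benefits of chemotherapy"), intervention rate 40%, one-sided type I error 2.5%, 194 patients (all Section 6.0), 1:1 allocation (Section 4.0). **Assumed:** 60% inaccurate at baseline in both arms, and a within-arm correlation phi between the baseline and follow-up answers. The documents give no value for phi.

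**1. The plan's own figure.** Pooled formula without continuity correction, mean rate 0.5:

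n per arm = [1.960 × √(2 × 0.5 × 0.5) + 0.842 × √(0.6 × 0.4 + 0.4 × 0.6)]² / 0.20² = (1.386 + 0.583)² / 0.04 = 96.9, so 97 per arm and 194 in total, with power 0.800. The stated figure reproduces.

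**2. The test actually named.** Enumerating all outcomes at 97 per arm, the one-sided Fisher test has exact power 0.764. It needs 102 per arm to reach 80%. With all 244 analysed (122 per arm) its power is 0.849.

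**3. Value of the baseline answer, by formula.** A covariate with within-arm correlation phi multiplies the residual variance by about (1 − phi²), which is equivalent to having 97/(1 − phi²) patients per arm.

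| phi | 1 − phi² | Equivalent n per arm | Power at N = 194 |
|---|---|---|---|
| 0.2 | 0.96 | 101.0 | 0.816 |
| 0.3 | 0.91 | 106.6 | 0.837 |
| 0.4 | 0.84 | 115.5 | 0.865 |
| 0.5 | 0.75 | 129.3 | 0.900 |

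**4. Check by simulation.** Mantel-Haenszel test stratified by the baseline answer, 97 per arm, 60% v 40%: power about 0.81 / 0.83 / 0.86 / 0.90 at phi 0.2 / 0.3 / 0.4 / 0.5, against about 0.81 for the unadjusted chi-square test in the same runs. Rejection under the null stays near 2.5%.

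**5. Splitting the gain.** Moving from Fisher to an unadjusted chi-square test accounts for 0.800 − 0.764, or about 4 points. The rest comes from the baseline answer: about 1 point at phi 0.2 and 10 points at phi 0.5. An exact stratified test would keep some of Fisher's conservatism, so the simulated figures belong to the Mantel-Haenszel version.

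**6. Ceiling on phi.** With 60% inaccurate at baseline and 40% at follow-up in the intervention arm, the largest possible phi is (0.40 − 0.60 × 0.40)/√(0.24 × 0.24) = 0.16/0.24 = 0.67. A value of 0.5 is therefore 75% of the maximum.

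**7. Chance imbalance.** The standard error of the baseline difference is √(2 × 0.24/97) = 0.070. A difference above 10 points in either direction is 1.42 standard errors and occurs in about 16% of trials.

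**The case against.** The strongest reply is that this is one missing table mark plus an analytic preference.

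- The summaries in Sections 5.2 and 5.7 work at domain level. They also leave out quality of life, optimism and health literacy, all marked at baseline in the table. They do list illness understanding, a domain that Section 5.2 ties to curability on the post-decision survey.
- The table is imperfect: the adequate-information row has no mark at any time point, although the text says patients are asked about it. The item-specific sentence in Section 5.4 may be the better guide.
- The unadjusted test is valid, and the sample size was set for an unadjusted comparison.
- Baseline answers given after unblinded randomization may already reflect the tools. Answers from patients enrolled during first-line treatment may be old and concern another regimen.

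Most of this stands, and it limits the point. A reader might infer that the baseline item has been dropped from the survey. The documents do not show that, because the baseline form is listed as Appendix C but not supplied. A reader might also infer that change in the cure belief cannot be measured. It can be, from post-decision to follow-up, even on the table's reading. Nor is there a case for bias or for a wrong stated sample size.

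The reply does not remove the conflict between the text and the table on the primary item. It also does not explain why an answer the protocol says it collects has no planned use. The imputation plan names no variables, so it neither excludes nor includes this one. The timing problems call for a rule on which answers to use; they are not a reason to discard the sound ones.

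**Conclusion.** The concern holds in a limited form. Section 5.4 contradicts its own table on whether the primary item is asked at baseline, and the supplied text cannot resolve it. The primary comparison is unadjusted, which costs precision but not validity.

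At 97 per arm and 60% v 40%, power would rise from about 80% (chi-square) or 76% (planned Fisher test) to about 81% to 90% for an assumed correlation of 0.2 to 0.5. At the low end, nearly all of the improvement over Fisher comes from leaving that test. These figures assume complete baseline answers given before randomization. The gain will be smaller where answers are missing, late or given long before randomization.

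**What to change.** 1. Check the baseline form. Bring the Section 5.4 table and the summaries in Sections 5.2 and 5.7 into line with the Section 5.4 text, so that the cure item is on the baseline survey and shown there.
2. In Section 6.0, make the primary comparison a Mantel-Haenszel or exact stratified test, with strata formed by the pre-randomization answer (accurate, inaccurate, missing) and line of therapy, the stratification factor in Section 4.0.
3. Treat baseline answers given after randomization, as Section 5.5 allows, as missing for this adjustment.
4. Name the pre-randomization answer in the imputation model.
5. Do not make the item mandatory: Section 5.6 lets participants skip questions that they find discomforting.

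The cost is a few lines of text, one item that the protocol already promises, and slightly more analysis work. The allowance for late baseline completion can stay; it only reduces the gain for those patients.
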